#### 14.1.1. ALL AEs

Incidence of TEAEs will be presented in frequency tables, sorted by SOC and PT in alphabetical order and, if applicable, broken down further by maximum severity.

Each participant will be counted only once within each PT or SOC. If a participant experiences more than one TEAE within a PT or SOC, only the TEAE with the strongest relationship or the worst severity, as appropriate, will be included in the summaries of

Document: [\\quintiles.net\Enterprise\Apps\sasdata\SAS\sas\GSK\GSK4045154\PZAA7715\Biostatistics\Documentation\SAP\GSK\\_213152\\_PZAA7715\\_SAP\\_Final\\_v1.0\\_07SEP2022](\\quintiles.net\Enterprise\Apps\sasdata\SAS\sas\GSK\GSK4045154\PZAA7715\Biostatistics\Documentation\SAP\GSK_213152_PZAA7715_SAP_Final_v1.0_07SEP2022)

Author: PPD Version Number: 1.0  
Version Date: 07SEP2022

Template No.: CS\_TP\_BS016 Revision 6 Reference: CS\_WI\_BS005

Effective Date: 02Dec2019

relationship and severity.

#### 14.1.1.1. Severity

Severity is classified by grade according to the investigator as grade 1 (mild)/ grade 2 (moderate)/ grade 3 (severe)/ grade 4 (life threatening)/ grade 5 (death related to AE)(increasing severity). AEs will be graded using the NCI-CTCAE v5 grading as per the American Society of Clinical Oncology (ASCO) guidelines (NCI-CTCAE v5, 2017). Grading will be recorded in the “Adverse Events” form of the eCRF.

If a participant reports a TEAE more than once within that SOC/ PT, the AE with the worst-case grade will be used in the corresponding summaries. In case a participant had events with missing and non-missing grades, the maximum of the non-missing grades will be displayed.

[figure not shown]

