### 14.1. ADVERSE EVENTS

Adverse Events (AEs) will be coded using MedDRA V23.0 or later.

Treatment emergent adverse events (TEAEs) are defined as AEs that started or worsened in severity during the on-treatment period, as defined in Section 6.3.1. However, for the first administration of the study treatment, if the AE Start Date is equal to that date, then AEs with the field “Timing related to Bintrafusp alfa” flagged as “Before” on the “Adverse Events Details” form of the eCRF would not be considered a TEAE.

Changes in toxicity grade, seriousness or outcome of AEs are recorded as separate entries in the eCRF with associated end and start dates (start date is equal to or 1 day greater than end date of previous entry). Such entries reporting the same event in such immediately consecutive periods will be considered as one event in the analysis. These events will be kept as separate records in the database and the listing in order to maintain the full detailed history of the events. For tables, the start date of the first treatment emergent record in the sequence is taken as start date of the entire event, similarly the end date of the last event in the

Document: [\\quintiles.net\Enterprise\Apps\sasdata\SAS\sas\GSK\GSK4045154\PZAA7715\Biostatistics\Documentation\SAP\GSK\\_213152\\_PZAA7715\\_SAP\\_Final\\_v1.0\\_07SEP2022](\\quintiles.net\Enterprise\Apps\sasdata\SAS\sas\GSK\GSK4045154\PZAA7715\Biostatistics\Documentation\SAP\GSK_213152_PZAA7715_SAP_Final_v1.0_07SEP2022)

Author: PPD Version Number: 1.0

Version Date: 07SEP2022

Template No.: CS\_TP\_BS016 Revision 6

Reference: CS\_WI\_BS005

Effective Date: 02Dec2019

sequence is taken as end date of the entire event. The overall outcome of the adverse event is the outcome of the last event in the sequence. Duration of the AE and the TEAE flag will be adjusted accordingly in the analysis.

See Appendix 2 for handling of partial dates for AEs. In the case where it is not possible to define an AE as treatment emergent or not, the AE will be classified by the worst-case; i.e. treatment emergent.

An overall summary of number and percentage of participants within each of the following categories will be provided:

- Any TEAE
- Any related TEAE
- Any serious TEAE
- Any related serious TEAE
- Any grade  $\geq 3$  TEAE
- Any related grade  $\geq 3$  TEAE
- Any grade  $\geq 4$  TEAE
- Any related grade  $\geq 4$  TEAE
- Any TEAE Leading to Death
- Any related TEAE Leading to Death

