#### 14.1.1.2. Relationship to Study Treatment

Relationship to study treatment is determined by the investigator. TEAEs with a missing relationship to study treatment will be regarded as “*Related*” to study treatment. If a participant reports the same AE more than once within that SOC/ PT, the AE with the worst-case relationship to study treatment will be used in the corresponding relationship summaries.

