#### **14.1.4. SERIOUS ADVERSE EVENTS**

Serious adverse events (SAEs) are those events recorded as “Serious” on the “Adverse Events” form of the eCRF. TEAEs with missing seriousness will be considered as serious.

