## 14.2. DEATHS

All deaths, deaths within 30 days after last dose of study treatment, death within 60 days after first dose of study treatment (for all participants, the first dose will be the first dose of the first treatment phase) as well as the primary reason for death will be tabulated based on information from the “Death” eCRF forms.

The following summaries will be provided:

- Number of deaths

Document: [\\quintiles.net\\Enterprise\\Apps\\sasdata\\SAs\\sas\\GSK\\GSK4045154\\PZAA7715\\Biostatistics\\Documentation\\SAP\\GSK\\_213152\\_PZAA7715\\_SAP\\_Final\\_v1.0\\_07SEP2022](\\quintiles.net\\Enterprise\\Apps\\sasdata\\SAs\\sas\\GSK\\GSK4045154\\PZAA7715\\Biostatistics\\Documentation\\SAP\\GSK_213152_PZAA7715_SAP_Final_v1.0_07SEP2022)

Author: PPD Version Number: 1.0  
Version Date: 07SEP2022

Template No.: CS\_TP\_BS016 Revision 6 Reference: CS\_WI\_BS005

Effective Date: 02Dec2019

- Number of deaths within 30 days after last dose of study treatment
- Number of deaths within 60 days after first dose of study treatment

Primary reason for death will be included in each of these sections with the following reasons:

- Progressive disease and/or disease related condition
- Event unrelated to study treatment
- Event related to study treatment
- Unknown.

In addition, date and cause of death will be provided in an individual participant data listing together with following dosing information: participant identifier, age, sex, race, date of first/last study treatment, number of infusions, day relative to the first and the last infusion, primary reason, autopsy (Y/N/U), AEs with fatal outcome (list preferred terms of AEs with outcome=Fatal, as well as Grade 5 or Serious resulting in death), flag for death within 30 days of last dose of study treatment and flag for death within 60 days of first dose of study treatment.

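### A TEAE that led to death but has no recorded grade can be shown at a milder grade and left out of the Grade ≥3 and ≥4 counts (SAP 14.1.1.1 with 7.3).

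*SAP*

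**What the plan says.** Severity of AEs by NCI-CTCAE v5 is part of the secondary endpoint (Protocol Section 3; SAP Table A). The relevant SAP provisions are these.

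- **Scale.** SAP 14.1.1.1 uses investigator grades, and the top of its scale reads "grade 4 (life threatening)/ grade 5 (death related to AE".
- **Several events.** "If a participant reports a TEAE more than once within that SOC/ PT, the AE with the worst-case grade will be used".
- **Blank grades.** "In case a participant had events with missing and non-missing grades, the maximum of the non-missing grades will be displayed". No exception is made for fatal or life-threatening events.
- **Default for missing data.** SAP 7.3 does not impute unless stated otherwise. SAP 6.6 shows missing observations as a separate category.
- **Fatal TEAEs.** SAP 14.1.5 accepts a fatal outcome, Grade 5, or a seriousness criterion of death. The first and third routes need no grade, and none of the three assigns one. The death listing in SAP 14.2 likewise picks up fatal outcomes "as well as Grade 5 or Serious resulting in death".
- **Records.** Under SAP 14.1, a change in grade, seriousness or outcome opens a new eCRF entry, and consecutive entries are analysed as one event. Start date, end date and outcome of the combined event are defined there; its grade is not.
- **Outputs.** The SAP 14.1 overview has rows for any TEAE of Grade ≥3, of Grade ≥4, and leading to death, each with a related counterpart. Grade ≥3 is also tabulated by SOC and PT, and worst grade is summarized.

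**The concern.** The SAP knows an event was fatal from one field, but ignores that knowledge when the grade field is blank. By the SAP's own scale an AE-related death is Grade 5, yet the worst-grade display could show Grade 1 or 2 for that participant.

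Three neighbouring gaps are resolved conservatively. When treatment emergence cannot be settled, "the AE will be classified by the worst-case; i.e. treatment emergent". For causality, "TEAEs with a missing relationship to study treatment will be regarded as" related. For seriousness, "TEAEs with missing seriousness will be considered as serious". Grade is handled differently and no reason is given.

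At stake are the severity tables, in a study whose reporting is cut back to the primary and secondary endpoints (Protocol Section 9), and the consistency of the overview. A reader who sees more participants under death than under Grade ≥4 would rightly question the table.

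**Working it through.** The plan states no figure that depends on this rule, so there is none to reproduce. The check applies the rules literally.

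**Inputs.** Displayed grade = maximum of the non-missing grades (SAP 14.1.1.1). No imputation (SAP 7.3). Death row by outcome, Grade 5 or seriousness criterion (SAP 14.1.5). Denominator 25 treated (Protocol 9.2).

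**Test cases**, one participant each, overall rows:

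| Participant's TEAEs | Worst grade shown | In Grade ≥3 | In Grade ≥4 | In death row | Worst grade after fix |
|---|---|---|---|---|---|
| Grade 1; ungraded fatal | 1 | no | no | yes | 5 |
| Grade 3; ungraded fatal | 3 | yes | no | yes | 5 |
| Ungraded fatal only | none | no | no | yes | 5 |
| Grade 2; ungraded life-threatening | 2 | no | no | no | 4 |
| Grade 4; ungraded, neither fatal nor life-threatening | 4 | yes | yes | no | 4 |

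**Two mechanisms.** The first and third rows separate them. The displayed Grade 1 comes from the maximum rule. Absence from the Grade ≥3 and ≥4 rows comes from non-imputation, because it also occurs when no other event is graded. A fix must therefore assign the grade, not merely alter how the maximum is taken.

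**Scope.** The sentence before the blank-grade rule works within SOC or PT. In SOC and PT rows, masking therefore needs a graded event in the same SOC or PT. An earlier record of the same event is enough: a Grade 2 entry followed by an ungraded fatal entry would be displayed as Grade 2. In the any-TEAE worst-grade display, any graded TEAE is enough.

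**Size.** One participant is 1/25 = 4.0 percentage points, and k such participants are k × 4.0 points. The documents give no count of blank grades, so k is unknown and may be 0. Illustrations with assumed counts (exact Clopper-Pearson 95% intervals, which the SAP does not plan for AE rates):

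- Grade ≥4: 0/25 = 0% (0 to 13.7) becomes 1/25 = 4.0% (0.1 to 20.4).
- Grade ≥4: 2/25 = 8.0% (1.0 to 26.0) becomes 3/25 = 12.0% (2.5 to 31.2).
- Grade ≥3: 5/25 = 20.0% (6.8 to 40.7) becomes 6/25 = 24.0% (9.4 to 45.1).

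The overall row moves only if the participant has no other TEAE at that grade. A SOC or PT row moves only if there is no other at that grade within it.

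**The case against.** The strongest reply is that the case may never arise and would be visible if it did. Protocol 10.3.4 requires an intensity assessment for every AE and SAE, and Protocol 10.1.5 provides ongoing source data verification. Fatal events remain in the death and serious-event outputs, and the SAP 14.1 listing shows grade, outcome and seriousness for every AE. All of that stands, and it keeps the point modest. It does not make the severity tables right if a blank survives to lock. Moreover, the intensity categories in Protocol 10.3.4 are mild, moderate and severe, with CTCAE mentioned only as a measure that may be used.

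Several stronger readings are tempting but unsupported:

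- **That the maximum rule itself removes participants from the Grade ≥3 and ≥4 rows.** It does not; SAP 7.3 does.
- **That every other missing AE attribute goes to the worst case.** Only the three named above do. Missing action taken is not read as drug withdrawn (SAP 14.1.2), missing outcome is not read as fatal (SAP 14.1.5), and some incomplete stop dates are left alone (SAP Appendix 2).
- **That the rule can only lower the reported grade.** Compared with the missing category of SAP 6.6, it preserves a known grade: Grade 3 plus a blank shows Grade 3. That is a good reason to keep it for ordinary blanks.
- **That every Grade ≥3 or ≥4 row shifts by 4.0 points.** Only the overall row and the event's own SOC and PT rows can.
- **That the several routes in SAP 14.1.5 show blank-grade deaths are expected.** They equally cover a fatal event recorded below Grade 5, which is a data query and not a missing grade.

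**Conclusion.** The point holds in a limited form. As written, the SAP can count a TEAE as leading to death while displaying it at a milder grade and omitting it from the Grade ≥3 and ≥4 counts. An ungraded life-threatening event is exposed to the same understatement. The effect is 0 if no grades are blank, and otherwise at most 4.0 points per affected participant in the rows described. No death is lost from the report.

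This rests on reading 14.1.1.1 and 7.3 literally, on 25 treated participants, and on at least one relevant blank remaining at lock. The last is possible but not shown by the documents. It is a cheap correction to a rule that can give a wrong severity; it does not suggest that the safety data are unreliable.

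**What to change.** Add to SAP 14.1.1.1, before the existing sentence on missing grades:

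> For grade summaries, a TEAE with missing grade is assigned Grade 5 if it meets the 14.1.5 definition of leading to death, and Grade 4 if its seriousness criterion is life-threatening.

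Grade 5 takes precedence where both apply. Make the assignment on each eCRF record before consecutive records are combined; otherwise an earlier graded record would mask the blank. This assumes the eCRF seriousness criteria include life-threatening, as the SAE definition in Protocol 10.3.2 does.

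Keep the maximum-of-non-missing rule for all other blanks. Moving those participants to a missing category would hide known Grade 3 or 4 events and set the worst-grade table against the Grade ≥3 and ≥4 rows. Footnote the number of participants with any remaining ungraded TEAE. Querying blank grades before lock is a sensible complement.

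The cost is one sentence, one programming step on 25 participants and a footnote. Grade ≥3 and ≥4 counts may be slightly higher. A few grades would be derived by program and not recorded by the investigator, so they should be flagged in the AE listing. If no grades are blank, the reported counts do not change.

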#### 14.1.1.2. Relationship to Study Treatment

Relationship to study treatment is determined by the investigator. TEAEs with a missing relationship to study treatment will be regarded as “*Related*” to study treatment. If a participant reports the same AE more than once within that SOC/ PT, the AE with the worst-case relationship to study treatment will be used in the corresponding relationship summaries.

### 14.1.2. TEAEs LEADING TO TEMPORARY TREATMENT INTERRUPTION AND WITHDRAWAL OF STUDY TREATMENT

For TEAEs leading to treatment interruption, modification or discontinuation of study treatment, the following incidence rates (frequencies and percentages) will be summarized in an overview table:

- TEAEs leading to temporary treatment interruption
- Related TEAEs leading to temporary treatment interruption
- TEAEs leading to permanent treatment discontinuation
- Related TEAEs leading to permanent treatment discontinuation
- TEAEs leading to infusion rate reduction
- Related TEAEs leading to infusion rate reduction.

Document: [\\quintiles.net\Enterprise\Apps\sasdata\SAS\sas\GSK\GSK4045154\PZAA7715\Biostatistics\Documentation\SAP\GSK\\_213152\\_PZAA7715\\_SAP\\_Final\\_v1.0\\_07SEP2022](\\quintiles.net\Enterprise\Apps\sasdata\SAS\sas\GSK\GSK4045154\PZAA7715\Biostatistics\Documentation\SAP\GSK_213152_PZAA7715_SAP_Final_v1.0_07SEP2022)  
Author: 

Version Number: 1.0

Version Date: 07SEP2022

Template No.: CS\_TP\_BS016 Revision 6

Reference: CS\_WI\_BS005

Effective Date: 02Dec2019

TEAEs leading to temporary treatment interruption will be identified by using the response for Action Taken of “Drug Interrupted” on the “Adverse Events Details” page of the eCRF. TEAEs leading to permanent discontinuation of study treatment will be identified by using the response for Action Taken of “Drug Withdrawn” on the “Adverse Events Details” form of the eCRF. TEAEs leading to infusion rate reduction will be identified by using the response for Other Action Taken of “Rate Reduced” on the “Adverse Events Details” page of the eCRF.

#### **14.1.3. TEAEs LEADING TO STUDY TERMINATION**

TEAEs leading to study termination will be identified by using the response for Other Action Taken of “Led to study termination” on the “Adverse Events Details” page of the eCRF.

#### **14.1.4. SERIOUS ADVERSE EVENTS**

Serious adverse events (SAEs) are those events recorded as “Serious” on the “Adverse Events” form of the eCRF. TEAEs with missing seriousness will be considered as serious.

#### **14.1.5. AEs LEADING TO DEATH**

TEAEs leading to Death are those events which are recorded as change in grade =”No” and outcome=“Fatal” or Grade=“Grade 5 or death related to AE” or serious adverse event=“Yes” and seriousness criteria include “Results in death” as the response for Outcome on the “Adverse Event Details” form of the eCRF.

#### **14.1.6. AEs OF SPECIAL INTEREST**

AEs of Special Interest (AESI) will be identified by a standardized list of MedDRA preferred terms to be updated on an ongoing basis during the study. The AESIs defined for this study are:

- Infusion-related Reactions
- Immune-related AEs
- TGF- $\beta$  inhibition mediated skin events including skin lesions

Document: [\\quintiles.net\\Enterprise\\Apps\\sasdata\\SAS\\sas\\GSK\\GSK4045154\\PZAA7715\\Biostatistics\\Documentation\\SAP\\GSK\\_213152\\_PZAA7715\\_SAP\\_Final\\_v1.0\\_07SEP2022](\\quintiles.net\\Enterprise\\Apps\\sasdata\\SAS\\sas\\GSK\\GSK4045154\\PZAA7715\\Biostatistics\\Documentation\\SAP\\GSK_213152_PZAA7715_SAP_Final_v1.0_07SEP2022)

Author: PPD Version Number: 1.0  
Version Date: 07SEP2022

Template No.: CS\_TP\_BS016 Revision 6

Reference: CS\_WI\_BS005

Effective Date: 02Dec2019

- Treatment related Anemia
- Bleeding events
- Wound healing delay
- Secondary malignancies
- Embryofetal toxicities.

Further details of the derivation of the AESI can be found in Appendix 3.

#### 14.1.6.1. Infusion-related Reactions Including Immediate Hypersensitivity

Infusion-Related Reactions (IRRs) are defined as AEs with PTs according to a pre-specified MedDRA search list, and are divided into two subcategories: “reactions” and “signs and symptoms” based on criteria on the timely relationship as detailed in Appendix 3.

The listing of IRRs will display the study drug administration modification details together with the infusion-related adverse event including administration date (day) /time, reason for modification, type of modification, modification start time, use of premedication, IRR AE Preferred Term, IRR AE grade, IRR AE start day /stop day, IRR AE time related to infusion.

#### 14.1.6.2. Immune-related AEs

Immune-related adverse events (irAEs) will be identified programmatically as detailed in Appendix 3.

The frequency table of immune-related AEs by worst grade and PT will be provided.

#### 14.1.6.3. Potential TGF $\beta$ -mediated Skin AEs

Identification of skin AEs possibly related to TGF $\beta$  inhibition is detailed in appendix 3.

Frequency tables for TGF $\beta$ -mediated skin TEAEs leading to permanent treatment discontinuation and serious TGF $\beta$ -mediated skin TEAEs will be provided by MedDRA PTs (including both narrow and broad definition PTs).

Document: [\\quintiles.net\Enterprise\Apps\sasdata\SAS\sas\GSK\GSK4045154\PZAA7715\Biostatistics\Documentation\SAP\GSK\\_213152\\_PZAA7715\\_SAP\\_Final\\_v1.0\\_07SEP2022](\\quintiles.net\Enterprise\Apps\sasdata\SAS\sas\GSK\GSK4045154\PZAA7715\Biostatistics\Documentation\SAP\GSK_213152_PZAA7715_SAP_Final_v1.0_07SEP2022)

Author: PPD Version Number: 1.0  
Version Date: 07SEP2022

Template No.: CS\_TP\_BS016 Revision 6

Reference: CS\_WI\_BS005

Effective Date: 02Dec2019

#### 14.1.6.4. Treatment related Anemia

Treatment related anemia AEs will be identified as described in Appendix 3.

#### 14.1.6.5. Bleeding Events

Bleeding events are classified by the MedDRA SMQ Hemorrhage terms (excluding laboratory terms) and will be summarized separately for TEAEs and related TEAEs by SOC and PT.

#### 14.1.6.6. Wound Healing Delay

Derivation of wound healing delay AEs can be found in Appendix 3..

#### 14.1.6.7. Secondary Malignancies

Details of the determination of secondary malignancies can be found in Appendix 3.

#### 14.1.6.8. Embryofetal Toxicities

Embryofetal Toxicities will not be derived as the occurrence of this AE is not considered a likely event due to measures of contraception and few participants at an age of child-bearing potential.

## 14.2. DEATHS

All deaths, deaths within 30 days after last dose of study treatment, death within 60 days after first dose of study treatment (for all participants, the first dose will be the first dose of the first treatment phase) as well as the primary reason for death will be tabulated based on information from the “Death” eCRF forms.

The following summaries will be provided:

- Number of deaths

Document: [\\quintiles.net\\Enterprise\\Apps\\sasdata\\SAs\\sas\\GSK\\GSK4045154\\PZAA7715\\Biostatistics\\Documentation\\SAP\\GSK\\_213152\\_PZAA7715\\_SAP\\_Final\\_v1.0\\_07SEP2022](\\quintiles.net\\Enterprise\\Apps\\sasdata\\SAs\\sas\\GSK\\GSK4045154\\PZAA7715\\Biostatistics\\Documentation\\SAP\\GSK_213152_PZAA7715_SAP_Final_v1.0_07SEP2022)

Author: PPD Version Number: 1.0  
Version Date: 07SEP2022

Template No.: CS\_TP\_BS016 Revision 6 Reference: CS\_WI\_BS005

Effective Date: 02Dec2019

- Number of deaths within 30 days after last dose of study treatment
- Number of deaths within 60 days after first dose of study treatment

Primary reason for death will be included in each of these sections with the following reasons:

- Progressive disease and/or disease related condition
- Event unrelated to study treatment
- Event related to study treatment
- Unknown.

In addition, date and cause of death will be provided in an individual participant data listing together with following dosing information: participant identifier, age, sex, race, date of first/last study treatment, number of infusions, day relative to the first and the last infusion, primary reason, autopsy (Y/N/U), AEs with fatal outcome (list preferred terms of AEs with outcome=Fatal, as well as Grade 5 or Serious resulting in death), flag for death within 30 days of last dose of study treatment and flag for death within 60 days of first dose of study treatment.

### 14.3. LABORATORY EVALUATIONS

Results from local laboratories will be included in the reporting of this study for Hematology, Biochemistry, Urinalysis, Coagulation, Thyroid Panel and Screening Tests and will be entered in the corresponding eCRF forms. [REDACTED]

[REDACTED] A list of laboratory assessments to be included in the outputs is included in the Protocol, Section 10.2, Appendix 2, Table 6.

A listing of hematology, biochemistry and coagulation will be created. This listing will include: participant identifier, age, sex, race, first dose date, last dose date, laboratory parameter (SI units), visit, collection date/time/day, International System of Units (SI) value, lower limit of normal (LLN), upper limit of normal (ULN), indicator of normal range (low, normal, high), toxicity term/grade according to NCI-CTCAE (when applicable) and highest/lowest on treatment value flag. Baseline and post-baseline values after the on-treatment period will be flagged. The on-treatment period is defined in Section 6.3.1. The listing will be sorted by participant identifier, parameter and laboratory measurement date.

T4 and TSH will be recorded in the "Hormonal Tests" form of the eCRF. Results will be

Document: [\\quintiles.net\Enterprise\Apps\sasdata\SAS\sas\GSK\GSK4045154\PZAA7715\Biostatistics\Documentation\SAP\GSK\\_213152\\_PZAA7715\\_SAP\\_Final\\_v1.0\\_07SEP2022](\\quintiles.net\Enterprise\Apps\sasdata\SAS\sas\GSK\GSK4045154\PZAA7715\Biostatistics\Documentation\SAP\GSK_213152_PZAA7715_SAP_Final_v1.0_07SEP2022)

Author: PPD Version Number: 1.0  
Version Date: 07SEP2022

Template No.: CS\_TP\_BS016 Revision 6 Reference: CS\_WI\_BS005

Effective Date: 02Dec2019

included in the listing. Screening tests including pregnancy tests, and serology data will also be listed from the eCRF.

